4.1.2. Recruitment and Reimbursement of Patient Participants

Across all study phases, a target of 315 patients will participate in the study: 30 participants in Phase I (Qualitative Study); 24 focus group participants, 6 mock training participants); 168 patients in Phase II (Provider Training Study); and 144 in Phase III (Patient Training Study); 24 patients in the exploratory focus groups, and 5 in the cognitive interviews.

Candidates for Phase I (qualitative study/mock training) and for the exploratory focus groups will be recruited primarily through advertisements both internally via clinics at Fox Chase/Temple and externally via established community partners and other sites, telephone, and in-person at clinic at Fox Chase or Temple after identification through providers' schedules, or after identification through the Fox Chase Cancer Registry, using a study introductory letter (see supplemental materials). For patients identified through the Registry, patient lists will be approved by the patients' physician prior to sending the introductory letter. Given an approximately 20% no-show rate for the qualitative focus groups, we will recruit and schedule between 5 to 8 patients for focus groups, assuming that several candidates will not

show. Thus, the final sample size for patients may differ slightly from our estimate. Approximately twenty-four patients will participate in focus groups or interviews (three focus groups with approximately 8 patients per group) in both Phase I and the exploratory aim (for a total of approximately 48 patients over six focus groups), a new group of 6 patients will participate in the mock training sessions (range of 5-8, depending on adequacy of information received), and a new group of approximately 5 patients with the same inclusion criteria as the exploratory focus groups will participate in cognitive interviews (similar in procedure to the mock trainings; range of 4-6, depending on adequacy of information received). Larger groups present significant difficulties for recruitment and scheduling, and may be less preferable to more intimately sized groups given the sensitive topic of discussion. If adequate qualitative information is not obtained from the patient focus groups, additional focus groups may be held until the data have reached “saturation” (i.e., no substantial new information is gained; maximum of 2 focus groups per aim). Potential candidates who have not called to opt out of the study or otherwise opted out will be called or approached by a research member to confirm their eligibility. Screening will determine eligibility (see recruitment script in supplemental materials).

Candidates for Phase II (Provider Training Study) will be identified in advance through providers’ schedules and will be recruited primarily in-person in the clinic or through contact with a study letter prior to their planned visit. Pre-screening by the study team will identify candidates who are eligible and the patient’s provider will give final approval for approaching the patient. No separate screening is necessary. Candidates will have the opportunity to opt out either in-person, or over the telephone if contacted through the study letter in advance of their visit. For Phase III (Patient Training Study; N=144), recruitment will primarily be conducted through contact with a study letter for pre-screened patients approved by provider for contact in advance (generally 2-4 weeks) of a scheduled visit with a trained provider. Patients will have the opportunity to opt out as described above. A telephone screening call by the study team will confirm patient eligibility and assess accessibility of computer/devices, include a brief assessment of socio-demographic and medical characteristics, and health-related quality of life (e.g., level of sexual concerns, pain, fatigue), and include a detailed discussion of the study procedures. Advertisements may also be used for these phases, as needed.

For participating in Phase I (focus group/interview or mock training) or in the exploratory focus groups or cognitive interviews, participants will receive \$75. Patients participating in Phase II (Provider Training Study) will receive \$10 in compensation for completing the self-report materials and allowing us to assess communication during their clinic visit. For participating in Phase III, patients will receive \$60 for completing the self-report materials. Compensation will be provided in the form of gift cards, which will be given to patients at the time of completion of each of the 3 assessments (\$20 each; \$60 total).

4.2. Inclusion and Exclusion Criteria for Provider Participants

Inclusion criteria for provider participants are presented in the following table. An exception is denoted in the table below and with an asterisk. Note that in Phase II, fellows, nurses, students, and other third parties are consenting only to have us audio record their visits, and not to participate in the provider training, and therefore we have not included information about their eligibility for provider participants below.

Inclusion Criteria for Providers
• Is an oncologist or advanced practice clinician (Nurse Practitioner, Physician Assistant) who treats breast cancer patients (Phase I qualitative interview and Phases II and III)
OR
• Is an oncology fellow who treats breast cancer patients (Phase I mock training)
• Agrees to have interview audio recorded*

*Not necessary for inclusion into the Phase I (Qualitative Study) mock trainings, which will not be audio recorded

4.2.1. Inclusion and Exclusion Criteria for Patient Participants

The eligibility criteria for patient participants for all three phases of the study are presented in the table below. The slight differences in inclusion criteria for the different phases of the study are denoted.

Inclusion Criteria

• Female• Age \geq 21 years• For Phase I: Receiving any treatment for breast cancer or have completed acute treatment for breast cancer $<$ 5 years ago*
OR

• For Phase II or III: Receiving any treatment for breast cancer or have completed acute treatment for breast cancer $<$ 10 years ago• Attending clinic visits in the course of follow-up care (i.e., not an initial consult visit)• Score of \geq 3 on Patient Care Monitor Sexual Concerns screening item**• Willing to have focus group or clinic visit audio recorded, if the Phase II provider has consented to audio recording***
Exclusion Criteria

• Not able to speak English• ECOG Performance score $>$ 2 OR too ill to participate as judged by physician, self-report, or observation of the research team member• Overt cognitive dysfunction or psychiatric disturbance or severe mental illness (e.g., dementia, suicidal behavior, or psychosis), as observed or judged by the researcher or referring source.

*Phase I mock training participants may be within 10 years of completing treatment for breast cancer

**Only necessary for inclusion into Phase I and exploratory focus groups

[figure not shown]
***Not necessary for inclusion into the mock trainings within Phase I (Qualitative Study) or the cognitive interviews, which will not be audio recorded

With respect to inclusion criteria for the exploratory focus groups and cognitive interviews, because post-treatment breast cancer survivors who are partnered are most severely impacted by sexual problems and are more likely to participate in an intensive couple-based intervention addressing sexual concerns, the three exploratory focus groups and cognitive interviews are designed to concentrate on this subgroup and therefore patients participating in these groups/interviews will meet the following criteria: a) has Stage I-III cancer; b) completed active treatment (e.g., chemotherapy, radiation, surgery) 6 months-5 years ago (current use of endocrine therapy is acceptable); and d) lives with a romantic partner \geq 6 months (see recruiting script; in addition to being female, age \geq 21 years, scoring \geq 3 on PCM sexual concerns screening item, and being willing to have focus group audio recorded). Exclusion criteria for patients in the exploratory focus groups and cognitive interviews are as presented in the table above.

With respect to patient inclusion into Phase III, the Phase I qualitative data suggested that this intervention may be equally relevant to patients currently undergoing acute treatment (e.g., chemotherapy). Therefore, we will allow patients who are undergoing acute treatment into Phase III. Women undergoing treatment are also included in Phase II because we are interested in understanding and improving provider communication about sexual concerns across the treatment trajectory, rather than within the post-treatment phase only. For most study phases and the exploratory aim, we limit inclusion to women who are within five years of completing acute treatment because most of the research on sexual concerns in this population has been done in survivors within this timeframe and because beyond 5 years, the relationship between the breast cancer and the sexual concerns may not be well-linked. However, continuation of

endocrine therapy is acceptable for patients in all study phases because the length of use of endocrine therapy is now up to 10 years and because use of endocrine therapies is significantly linked to ongoing sexual problems. In order to allow for the broadest range of dialogue data to be collected in Phases II and III, we will allow patients into the study who are up to 10 years post-treatment. Because of the extended duration of hormonal therapy regimens to 10 years, sexual concerns are relevant to women in this group. Because discussing sexual concerns at the time of the consult visit (i.e., when many women learn of their cancer) may not be appropriate or desirable, women who are in follow-up are targeted. We limit participation in the focus groups in Phase I/exploratory aim to women reporting some degree of sexual concerns through a one-item screener given by a member of the research team (Sexual Concerns Screener on the Patient Care Monitor), in order to target these women in the development of the Skills-based intervention or the telephone-based Intimacy Enhancement intervention. We recognize that the Skills-based intervention could be relevant to women with or without sexual concerns, and thus, we would like to ensure that women from both of these groups can review the materials in our Phase I mock trainings. Because we are most interested in providers' communication in Phase II (e.g., how often they raise sexual concerns), patients in this phase are not restricted to those with sexual concerns. The Skills-based patient intervention to be tested in Phase III has content that is applicable to a wider range of patients by covering both menopausal and sexual health. For this reason, we do not plan to screen for sexual concerns for inclusion to Phase III. By including women both with and without sexual concerns in the mock trainings for this intervention, we will ensure that the intervention is appropriate and relevant to both groups of women. The patient participants in this study are limited to women because men with breast cancer are likely to have very different sexual concerns than women with breast cancer; thus, separate efforts to develop interventions targeting the sexual concerns of men with breast cancer are most likely appropriate.

4.3. Overview of Study Procedures

The study design for this research study is detailed in the figure above (numbers of patients shown in the figure are approximate) and a timeline is shown in the table below. In Phase I, we will use qualitative methods to develop and expert review and mock trainings to refine provider and patient training programs designed to enhance patient-provider communication about sexual concerns. In Phase II, we will pilot test the provider training program for feasibility and impact on provider beliefs. Through examining clinic dialogue, we will examine pre-post change in providers' communication behaviors. In Phase III, we will evaluate the feasibility and impact of the patient training on patient beliefs and sexual and QOL outcomes compared with a Control condition in a randomized trial. We will compare the two study arms on patient communication behaviors. Follow-up data will be collected at 1- and 6-months (providers) or 2-months (patients) post-training. In an exploratory aim completed alongside Phase I, we will use qualitative methods to tailor an Intimacy Enhancement intervention to address the sexual concerns of breast cancer survivors. (Exploratory focus groups are not shown in the study figure but will occur during a similar time frame as Phase I; cognitive interviews to refine the material for the Intimacy Enhancement intervention will occur during a similar time frame as the Phase I mock trainings).

Study Phase	Research Timeline																								
	Year 1				Year 2				Year 3				Year 4				Year 5								
Q1	Q2	Q3	Q4	Q1	Q2	Q3	Q4	Q1	Q2	Q3	Q4	Q1	Q2	Q3	Q4	Q1	Q2	Q3	Q4						
Study I Develop and Refine Interventions	RRC/IRB approval; Qualitative data collection/analysis; Development/refinement of protocols; Manuscript																								
Study II Implement and Test Provider Training	BL recordings/data collection; Provider training and feasibility evaluations; Post-training recordings/data collection/analysis; Manuscript																								
Study III Implement and Test Patient Training													BL data collection; Conduct patient pilot trial with post-training recordings; Analyze data; Follow-up evaluations; Manuscript/R01												

4.3.1. Qualitative Study Design (Phase I)

4.3.1.1. Provider Involvement in Qualitative Study. A very brief 6-item demographic survey will be given to providers to complete immediately after consent and before participating in the qualitative interview or mock training (see supplemental materials for self-report measures). The duration of participation for providers in this phase of the study is one visit (see section 4.4.1 for detailed information on duration of participation by study phase).

Individual qualitative interviews (45 minutes) and mock trainings will be conducted for ease of scheduling. These will generally take place at the provider's own office, for convenience. After consenting for the interview, the qualitative interviewer will begin the interview using a structured qualitative guide. The qualitative interviews will be led by [name], who has experience conducting both qualitative interviews and focus groups or another trained member of the team. Qualitative interviews will be audio recorded so that they can be coded.

Mock training sessions will be conducted by [name] or a trained research team member and will consist of the fellow reading the program materials and responding to questions on the program content and format. Mock training sessions are expected to take 60-90 minutes, depending on the length of time it takes individual fellows to read and respond to the materials. They will also be asked to comment on the material "off the cuff" as opposed to in response to specific questions. The research team member who will be conducting the mock trainings will take notes on the comments and responses made by fellows during this session.

4.3.1.2. Patient Involvement in Qualitative Study. A very brief 15-item demographic survey will be given to patients to complete immediately after consent and before participating in the focus groups/interviews or mock training/cognitive interview (see supplemental materials). The duration of participation for patients in this phase of the study is one visit (see section 4.4.2 for detailed information on duration of participation by study phase for patients).

Six focus groups (90 minutes; see explanatory table) will be conducted in private conference rooms that can be reserved in advance, such as Conference Room B or P4031. A greater number of patients are included in Phase I focus groups relative to providers to reflect the variability in patients' experiences. To capture potentially significant differences in patient perspectives, a diverse sample will be included with respect to age, race/ethnicity, disease stage, and treatment. Within Phase I focus groups, two focus groups will be conducted with partnered patients (i.e., those who are married or in significant relationships) and one focus group will be conducted in unpartnered patients, to provide data on a range of types of sexual and intimacy concerns and because little is known about the preferences of unpartnered breast cancer patients for sexuality interventions. Additionally, in the exploratory focus groups, because younger women are at risk for worse sexual impairment^{9,12} and may therefore feel more comfortable in a group with other young participants, one focus group will be limited to women diagnosed at ≤ 45 years old; the remaining two groups will include women > 45 . Qualitative focus groups will be audio recorded so that they can

Overview of Study Focus Groups		
Study Phase/Aim	Focus Group #	Participants
Phase I	1	Partnered
Phase I	2	Partnered
Phase I	3	Unpartnered
Exploratory	1	Diagnosed > 45
Exploratory	2	Diagnosed > 45
Exploratory	3	Diagnosed ≤ 45

be coded in detail to generate qualitative themes. As mentioned previously, additional focus groups may be added if saturation has not been reached with the 3 groups per aim. Individual patient qualitative interviews may also be conducted in place of focus groups if necessary. Other than the format of the qualitative interview, the procedure will be the same (e.g., interview content/script, survey completion, same reimbursement). The PI or a trained interviewer will conduct these interviews.

Mock trainings and cognitive interviews (60-90 minutes) will include an in-depth reading of the program materials, review of materials, and feedback on format and content. [name], and/or a trained research team member, will conduct focus groups and patient mock trainings/cognitive interviews. Mock trainings and cognitive interviews will not be audio recorded, but the research team member will take notes actively on participant responses and participants will be asked to take notes in the material as they have thoughts or comments.

4.3.2. Provider Training Study Design (Phase II)

A self-report survey will be given to providers participating in this phase to complete soon after consent (generally within one week). The table below shows the schedule of self-report measures to be completed by providers participating in the Provider Training program. At baseline (pre-training), providers will report socio-demographic information and rate self-efficacy and outcome expectancies for communicating about sexual concerns with their breast cancer patients,⁶⁷ reliable measures of beliefs associated with communication behaviors, and the extent to which they endorse certain barriers (e.g., time pressures, etc.) as limiting their communication with breast cancer patients about sexual concerns. The items assessing barriers are taken from a published study in which they showed sensitivity to change through participation in a provider training intervention.⁶⁸ Providers will complete the measures of self-efficacy and outcome expectancies at three other time points: immediately post-training, and 1- and 6-month follow-ups. Efforts will be made to collect data at all time points in person using paper and pencil questionnaires from provider participants, although telephone, web, or mail-based paper administration may also be conducted if necessary.

Provider Training (Phase II) Self-Report Measures To Be Completed by Providers				
Measure	Baseline	Post-Training	1-Month Follow-up	6-Month Follow-up
Demographics (6 items)	X	-	-	-
Beliefs ⁶⁷	X	X	X	X
- Self-efficacy (3 items)				
- Outcome expectations (7 items)				
- Barriers (14 items)				
Feasibility and Acceptability Items	-	X (19 items)	X (14 items)	X (14 items)
Future Program Preferences	-	-	-	X (8 items)

Patients participating in this phase of the study will complete a survey immediately after the clinic visit that includes a socio-demographic questionnaire (6 items), health-related quality of life (HRQOL) items (8 items), and several questions assessing the communication that occurred during their clinic visit, that, together, is expected to take no more than 5-10 minutes to complete. The HRQOL information captures information that will help us interpret the communication findings, while the communication items will supplement the audio recorded communication data or replace it, in cases in which we cannot obtain audio recordings of the dialogue.

Provider Training Primary Learning Targets
• Gain familiarity with types and causes of common sexual complaints and medical/non-medical treatments
• Recognize barriers to effective P-P communication
• Learn patients' preferred communication
• Gain practice and confidence in stepped care model (PLISSIT), responding to negative reactions
• Gain awareness of available resources/referral options
• Learn how to address contextual/socio-cultural factors

Between eight to sixteen clinic visits with unique patients will be assessed for communication per provider in the baseline phase of the study, resulting in at least 48 baseline visits, although we will allow a provider to participate in the training program with fewer than 8 visits recorded if it seems unlikely that we will be able to obtain this target number of visits in a timely fashion (e.g., a provider's clinic schedule has changed) approximately the same number will be assessed for communication per provider with unique patients at post-training. Sessions will be assessed until enough sessions per provider have been obtained. For each study visit that is audio recorded, two audio recording devices will be positioned in the patient examination room to catch all dialogue.

After the baseline clinic visit assessment phase is complete, as many of the Phase II providers as are willing will participate in the provider training program (see explanatory table). The goal of the provider training program is not to make providers proficient in sexual counseling. Rather, the program will focus on the first two stages of the stepped care PLISSIT model for addressing sexual concerns,⁶⁹ i.e., 1) offering permission to patients to discuss sexuality, in this case by asking about sexuality or sexual concerns, and 2) offering limited information about sexual concerns. These communication behaviors are consistent with the 2013 NCCN Clinical Practice Guidelines in Survivorship for addressing cancer survivors' sexual function^{4,70} by targeting the identification of patients' sexual concerns.

Training is planned to consist of two complementary components: an educational component (e.g., informational workbook with supplemental clips or slides) and a 30-60-minute (approximate) in-person workshop, conducted in groups or pairs that will include review of material on communication about sexual concerns, viewing slides and/or videos with sample patient-clinician exchanges, and engaging in skills practice, which could consist of role-plays, discussions or drill-type exercises, and feedback, valuable techniques in communication skills development (see Table above).⁷¹⁻⁷³ If scheduling small groups or pairs appears prohibitive, alternative approaches will be explored including individual training sessions, and two sessions may be planned if it appears difficult to cover all the material in one session. The training program will also aim to increase provider awareness of resources for in-depth information (e.g., supplying providers with pamphlets, pocket information cards, etc.)⁷⁴ and further assessment through referral to the Fox Chase Sexual Health and Menopause Clinic or elsewhere. The small group sessions will be audio recorded to facilitate post-training feasibility analyses. Following training, providers may receive periodic (e.g., weekly) emails designed to reinforce content and skills containing reminders about skills, communication tips, communication video clips, new research about sexuality in breast cancer, or quotations from interactions illustrating good/poor communication.

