In Phase I, we anticipate enrolling 8 oncologists and 4 nurse practitioners (NPs) who treat breast cancer patients from Fox Chase/Temple affiliates or other sites to participate in qualitative interviews. If adequate qualitative information is not obtained from these interviews, additional interviews (a maximum of 6) may be held with oncologists/nurse practitioners until the data have reached "saturation" (i.e., no substantial new information is gained); alternatively, if saturation is reached with fewer provider interviews (no less than 6 oncologists and 3 NP's), we may consider stopping recruitment early for this phase. A target of four oncology fellows from FCCC (range of 3-8, depending on the adequacy of information received) will participate in the mock training. A new group of 6-8 Fox Chase/Temple or partner site breast cancer providers, consisting of oncologists and advanced practice clinicians, e.g., Nurse Practitioners, Physician Assistants, who agree to have clinic visits with enrolled patients analyzed will complete the pilot training program (Phase II). To establish a pattern of provider behavior, 8-16 patients per provider will be recruited for all phases of the clinic visit assessment study (Phases II and III; see study design figure in section 4.3), however, due to the unpredictable nature of clinic schedules, we may ultimately recruit fewer than 8 or more than 16 patients for some providers (e.g., we may recruit more heavily from some clinics if other clinics do not offer enough eligible patients). We leave open a fairly wide range for the number of total audio recorded clinic visits per clinician because the total number needed will depend on the data obtained on our target outcome variables and on the number of clinicians who participate; if very few conversations occur regarding sexual concerns, we may need to record more clinic encounters. In the case that a provider participant who has consented to audio recording shares their clinic encounters with fellows, nurses, students, or another third party, those fellows will also be consented using separate consent forms so that their involvement in each clinic visit included in the study can be audio recorded.

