
Descriptive analyses (e.g., frequencies, measures of central tendency) will determine the feasibility and acceptability of the training program. Seventy-five percent of participants rating the training program favorably ("Agree"/"Strongly

Agree" or "Satisfied"/"Very Satisfied") on study evaluations will be considered adequate acceptability. Patients at baseline and post-intervention will be compared on socio-demographic and medical variables using Chi-square tests or t-tests. Pilot efficacy analyses will be calculated through the following method. Mean differences will be calculated in self-report outcome measures at baseline and 6-month follow-up as the final endpoint, along with standard deviations and the effect size (mean difference/SD of the differences). Regarding the communication outcomes, if audio recordings are available, those data will be used. If there appear to be significant differences between the audio recorded and the self-report communication data, separate analyses may be conducted for these two types of data. Clinician communication outcomes will be examined descriptively by comparing the proportions of clinic visits in which the target communication behaviors occurred at post-intervention versus baseline. Additionally, we will conduct exploratory analyses on the communication variables where the effect of post-intervention was evaluated using generalized linear models with robust standard errors via Generalized Estimating Equations to account for within-provider correlation. Specifically, logistic regression will be used to examine binary outcomes, Poisson regression will be used to examine length of discussion about sexual health and a risk ratio presented for this variable (no discussion was coded as zero seconds), and ordinal logistic regression will be used to examine intervention effects on complexity of communication (categorized as 0, 1, or 2) and on patient satisfaction. Although the study was not powered for formal comparisons, we will consider presenting the model based estimates of effect sizes and corresponding 95% confidence intervals.

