13.2.4. Sample Size Calculations

Because the objective of the Provider Training Study (Phase II) is to pilot test the newly developed provider training intervention, we do not conduct sample size calculations for this phase of the study, with the sample of 6-8 providers chosen based on what is feasible to accomplish in a pilot. Instead, sample size justification is provided below for the Patient Training Study. We will calculate pre-post effect sizes to inform a larger R01 trial that is expected to follow from this study.

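### The Phase II before/after communication contrast pools visits across providers, so a change in which providers contribute can bias it in either direction

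*Combined protocol and SAP*

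**What the plan says.** Section 4.3.2 sets the order of events. First, "Between eight to sixteen clinic visits with unique patients will be assessed for communication per provider in the baseline phase of the study". When that phase is complete, "as many of the Phase II providers as are willing will participate in the provider training program". After training, "approximately the same number will be assessed for communication per provider with unique patients at post-training". The lower limit on baseline visits can be waived: "we will allow a provider to participate in the training program with fewer than 8 visits recorded".

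Other sections describe training differently. Section 4.1.1 says that the 6-8 providers who agree to visit analysis will complete the training, and in section 17.0 the Phase II provider consent covers the intervention. Section 10.0 lets any participant leave at any time.

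Section 4.1.1 also allows heavier recruitment from some clinics than others. It explains the wide range of recordings per clinician by saying that "the total number needed will depend on the data obtained on our target outcome variables" and on how many clinicians take part.

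Section 13.2.3 examines clinician communication descriptively, by "comparing the proportions of clinic visits in which the target communication behaviors occurred at post-intervention versus baseline". It adds exploratory GEE models with robust standard errors for within-provider correlation. The working correlation is not stated. No section limits the contrast to providers seen in both periods, adds a provider term, or says what happens to the baseline visits of a provider who is not trained. Patients are to be compared across periods; providers are not.

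**The concern.** A pooled proportion is a visit-weighted average of provider rates. If the providers or their weights differ between the two periods, the pooled proportion moves even when no provider changes behaviour. A provider who supplies baseline visits and is then not trained is the clearest case.

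Provider communication behaviours are primary outcomes of Phase II (13.2.1) and the subject of Hypothesis I (2.3.1). Section 13.2.4 says that pre-post effect sizes will inform a larger trial, and 13.2.3 considers presenting model-based effects with 95% confidence intervals. A shift in mix would be carried into any such figure. The provider self-report outcomes do not share the problem, because their effect size is built from each provider's own change.

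**Working it through.** **The plan's own figure.** Section 4.3.2 gives a baseline total: "resulting in at least 48 baseline visits". With the smallest number of providers and visits, 6 × 8 = 48, so it reproduces. It is not a guaranteed floor, because fewer than 8 visits per provider is permitted. Phase II has no power calculation to reproduce: section 13.2.4 gives none, "with the sample of 6-8 providers chosen based on what is feasible to accomplish in a pilot".

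**Size of the mix effect.** Let P providers have equal visits at baseline, let d of them not be trained and have no post-training visits, and let training have no effect. With rate p_d in decliners and p_w in willing providers:

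- baseline = [d·p_d + (P − d)·p_w] / P
- post = p_w
- apparent gain = (d/P)·(p_w − p_d)

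P = 8 is from the plan. The rates and d are assumptions, since the documents give none. With p_d = 10% and p_w = 25%:

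- d = 1: baseline (0.10 + 7 × 0.25)/8 = 23.1%; gain 1.9 points
- d = 2: baseline (2 × 0.10 + 6 × 0.25)/8 = 21.25%; gain 3.75 points

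The sign follows p_w − p_d. With equal rates the gain is 0. With the rates reversed and d = 2, it is (2/8) × (0.10 − 0.25) = −3.75 points.

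Over a wider set of assumed pairs (5% v 35%, 10% v 40%, 20% v 40%), one to three decliners give 2.5 to 11.3 points with 8 providers and 3.3 to 15.0 points with 6.

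**Whether the GEE removes it.** Under an independence working correlation, the GEE odds ratio is the pooled one. For d = 2 above: (0.25/0.75)/(0.2125/0.7875) = 1.24 with no true effect. Other cases were simulated under no training effect (500 data sets each, 12 visits per provider per period). The last two columns are limited to providers seen in both periods; the restricted odds ratio uses independence.

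| Providers, decliners, rates | Pooled gain (points) | OR, independence | OR, exchangeable | Restricted gain (points) | Restricted OR |
|---|---|---|---|---|---|
| 8, 2, 5% v 35% | 7.7 | 1.43 | 1.33 | 0.2 | 1.01 |
| 8, 3, 5% v 35% | 10.7 | 1.69 | 1.42 | −0.6 | 0.97 |
| 6, 2, 5% v 35% | 9.6 | 1.59 | 1.40 | −0.3 | 0.98 |
| 8, 2, 20% v 40% | 5.0 | 1.24 | 1.23 | 0.1 | 1.01 |

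Exchangeable correlation reduces the distortion but does not remove it. Restriction does.

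**All providers trained, unequal visits.** Take four providers at 10% and four at 50%, with 12 visits each at baseline, then 8 from each low-rate and 16 from each high-rate provider afterwards. Baseline is 30.0%. Post is (4 × 8 × 0.10 + 4 × 16 × 0.50)/96 = 36.7%. That is a 6.7-point shift with no change in any provider. The average of the provider-specific differences is 0. This example departs from the aim of similar numbers per provider and shows only the mechanism.

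**The case against.** The strongest reply is that the plan expects every enrolled provider to be trained. Sections 4.1.1 and 17.0 support this, and in 4.1.1 the first payment is tied to surveys at the end of training. The wording about willing providers may only allow for dropout. That untrained providers have no post-training visits is inferred from the term itself, and 13.2.3 does not say outright that their baseline visits enter the comparison. This stands: a reader might infer a settled plan to train volunteers only and pool everyone at baseline, but the documents leave this open. If all are trained and retained, only unequal visit numbers remain.

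A reader might also infer from the visit-number clause in 4.1.1 that low communicators will be over-recorded at baseline. If two 10% providers had 16 visits and six 25% providers had 8, baseline would be (32 × 0.10 + 48 × 0.25)/80 = 19.0%, a false gain of 6.0 points. The documents do not support that reading. The clause explains a range of recordings across Phases II and III and names no provider-level or baseline-only trigger. In simulation, extending recording when conversations were few, with one common provider rate, left the pooled proportion at its true value (0.300 for 0.30; 0.100 for 0.10). Harm arises only if provider weights shift between periods.

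Finally, the comparison is descriptive in an unpowered pilot, and the bias is below sampling error. With 10 visits per provider and two decliners, the standard error ignoring clustering is √(0.2125 × 0.7875/80 + 0.25 × 0.75/60) = 7.2 points, against 3.75. This limits the seriousness but does not justify the method, because recording more visits from the same providers would not shrink the bias.

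**Conclusion.** The concern holds as a weakness in the stated method. Followed as written, 13.2.3 can mix provider composition into the before/after communication contrast, and the GEE as described does not prevent it. The illustrative size is about 2 to 4 points for one or two decliners of eight. This rests on assumed rates of 10% and 25%, equal visits, no true effect, and no post-training visits from decliners.

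A reader might infer that the training effect will be overstated. The documents do not support a direction: the bias is zero if decliners and willing providers have the same rate, and negative if decliners communicate more. The text should be changed, but in a descriptive pilot the matter is moderate. It does not concern the randomised comparison in Phase III.

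**What to change.** In 13.2.3:

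- Limit the before/after communication comparison, including the GEE models, to trained providers with visits in both periods.
- Make it within provider. Average the provider-specific post minus baseline differences, or add a provider term where event counts allow. With 6-8 providers and infrequent events, a provider term in a logistic model may cause separation; the averaged differences remain defined.
- Report untrained providers' baseline visits separately, with the number not trained and visit counts by provider and period.

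Reconcile 4.3.2 with 4.1.1 and 17.0 on whether all Phase II providers are trained.

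The visit-number clause in 4.1.1 need not change for this point. A change is probably too late for Phase II anyway, since 4.3.3 and 13.3.3 already draw on Phase II results. The analysis change can still be applied to data in hand.

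The cost is a few sentences and slightly less precision, because untrained providers' baseline visits leave the contrast; they still serve the baseline description. The change does not cure the small number of clusters. After restriction, the robust GEE test still rejected in about 10-16% of null data sets at a nominal 5%, so any intervals presented need a small-sample correction or a caveat.
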